6.7.5.2 Reactions to Dosing at Home

With the occurrence of symptoms of an acute reaction to IP after home-dosing, or any acute allergic reaction, subjects or parents/guardians are instructed to call the study site. The investigator must then determine whether or not the dose was tolerated ([Section 6.7.3](#)). Because of the reduced reliability inherent in the second-hand reporting of symptoms, investigators are strongly encouraged to have subjects return to the clinic to undergo dosing under direct observation whenever acute allergic symptoms associated with dosing are reported.

When symptoms of a dose-related allergic reaction are reported during the course of daily home-dosing, the investigator must assess the severity of the reaction and whether the dose associated with the reaction was tolerated. The appropriate intervention will depend on the type and severity of symptoms ([Figure 3](#)).

In general, moderate or severe symptoms will be considered clinically significant, and any dose eliciting such symptoms *assessed as not tolerated*; however, mild symptoms may also be considered clinically significant (eg, if affecting multiple organ systems, increasing in

intensity, occurring with increasing frequency, or affecting a larger area over time) and *assessed as not tolerated*. Whenever there is question as to the clinical significance of mild signs or symptoms, the investigator should have the subject return to the CRC for observed dosing under medical supervision.

For home-doses *assessed as not tolerated* on the basis of acute dose-related symptoms, the same procedures described in [Section 6.3.3](#) for adjusting up-dosing should be followed. Dose adjustment after administration of antihistamines or epinephrine for dose-related allergy symptoms is described in [Section 6.7.6](#).

The recurrence of mild symptoms over the course of several days of home-dosing should suggest that the dose level is not tolerated, even if each individual occurrence of symptoms could be assessed as tolerated on the basis of the criteria listed above. In this circumstance, investigator judgment will be required to determine the best course of action with the possible actions being the following:

[figure not shown]
- Continue with daily home dosing at the current dose level
- Continue the same daily dose for the rest of the 2-week interval, with the dose split into 2 fractional doses given 8 to 12 hours apart (the 2 fractional doses need not be equal)
- Return to the CRC for repeat dosing at the current dose level under direct observation to confirm whether or not the dose level is tolerated
- Return to the CRC for dosing of a previously tolerated dose level, either a 1- or 2-step reduction (per investigator judgment, based on severity of reaction) and follow the procedures described in [Section 6.7.5.2](#).
- Institute the 4-week hiatus from dosing, with resumption of dosing at the 3 mg/d dose level, as permitted for recurrent GI symptoms occurring at or before the 20 mg dose level, as described in [Section 6.7.3.2](#).
- Discontinuation of dosing

Any subject who discontinues up-dosing due to severe or repeated allergic reactions to IP should have his or her immune cell characterization blood draw and CBC ([Section 8](#)) at, or as nearly as possible to, the time of the last dose and no later than at their Early Discontinuation Visit.

6.7.5.3 Temporary Dose Adjustment in Response to Intercurrent Adverse Events

At the investigator's discretion, temporary dose reductions, ranging from a 1-step decrement (ie, to the previous dose) to approximately half of the current dose level (to the nearest feasible available whole dose), can be instituted as part of the treatment regimen for an intercurrent AE. Also, if a pattern of decreased tolerability of IP during menses is discerned, then a temporary dose reduction can be instituted during this time. The procedures for temporary dose reduction due to intercurrent AEs are provided in [Figure 4](#). Explanatory text follows the figure.

Figure 4: Schematic for Temporary Dose Reductions due to Intercurrent Adverse Events

Temporary dose reductions for intercurrent AEs may be instituted as follows:

- For dose reductions of **≤ 4 consecutive days**, whether dose re-escalation is to occur at home or in the CRC is at the investigator's discretion. If the reduction in dose is maintained for **≤ 4 consecutive days**, then the pre-reduction dose level (ie, the dose level last tolerated) may be resumed, with the biweekly escalation schedule kept unaltered.
- If a reduction in dose is maintained for **5 to 7 consecutive days**, then the subject is to return to the CRC to undergo dosing under medical supervision. At the investigator's discretion, the pre-reduction dose level may be resumed or dosing may continue at the reduced dose level. The biweekly escalation should be reset so that the subject receives at least 2 consecutive weeks of treatment at the dose level assigned (either the reduced or the pre-reduction dose level).
- If a reduction in dose is maintained for **8 to 14 consecutive days**, then the next escalation attempted must be conducted in the clinic, and it should only be to 1 dose level above the reduced dose. If the escalation is successful, the subject should continue home-dosing for a minimum of 2-weeks, with his or her biweekly escalation schedule reset as necessary.

Doses of IP may also be withheld at the investigator's discretion, in response to an intercurrent AE. Doses withheld as part of the treatment for an AE constitute a special category of missed peanut OIT doses ([Section 6.8](#)).

6.7.6 Treatment for Reactions During the Up-dosing Period: Pharmacological and Supportive Treatments

The treatments for reactions during the Up-dosing Period are summarized by severity of reaction in [Table 5](#).

Table 5: Treatment(s) for Reactions during the Up-dosing Period by Severity of Reaction

Reaction Severity ^a	Treatment(s)
Mild acute allergic reactions requiring treatment	Antihistamines
Moderate acute symptoms requiring treatment	Antihistamines and/or epinephrine, as indicated
Severe symptoms	Epinephrine

Assessment of severity of reaction is described in [Section 6.7.1](#). Assessment of tolerability of an individual dose is described in [Section 6.7.2](#).

- **General Approach:** Treatment of acute reactions should be with either an antihistamine and/or epinephrine, along with IV fluids, a beta-agonist (eg, albuterol, by inhaler or nebulizer), oxygen, and/or corticosteroids, as indicated.
- Many **mild** acute allergic reactions can be transient and self-limiting, requiring no therapeutic intervention. Others, however, may require treatment. Generally, for mild symptoms requiring treatment, the subject should receive antihistamines.
- Acute allergic reactions manifesting with **moderate** symptoms will generally require therapeutic intervention, although some, even moderate, symptoms may on rare occasion be so transient as to require no specific treatment. Generally, for moderate symptoms requiring treatment, the subjects should receive antihistamines and/or epinephrine, as indicated. If there is uncertainty as to the severity of the reaction, administering epinephrine would be considered the most appropriate course of action.
- Generally, **severe** symptoms will require treatment with epinephrine at a minimum.

The procedures(s) that should be implemented after treatment of a reaction experienced during the Up-dosing Period are summarized in [Table 6](#). An explanation follows the table.

Table 6: Procedure(s) Following Treatment of a Reaction Experienced during the Up-dosing Period

Treatment Given for a Reaction	Procedure(s) Following Treatment
Antihistamines only	Continue dose escalation
Epinephrine: 3 or more doses given for dose-related allergy symptoms or anaphylaxis	
 Stop study product dosing Subject is to return to the CRC 14 days after the last dose of study product for the Early Discontinuation Visit (Section 6.4)
Epinephrine given in CRC	
 Stop study product dosing Reduce next dose by 1 or 2 dose levels per investigator discretion based on the type and severity of the allergy symptoms (Section 6.7.5, Figure 3), and administer in the CRC After continuing the reduced dose after a duration of time recommended by the investigator, dose re-escalation at 1 dose level may be attempted in the CRC Following severe allergy symptoms, discussion with the medical monitor is strongly recommended
Epinephrine given at home	
 Instruct subjects to go to the nearest emergency department immediately Reduce next dose by 1 or 2 dose levels per investigator discretion based on the type and severity of the allergy symptoms (Section 6.7.5, Figure 3), and administer in the CRC under medical supervision prior to resuming any dosing at home Following severe allergy symptoms, discussion with the medical monitor is strongly recommended

CRC=clinical research center.

- Antihistamines

If a subject receives antihistamines only, the dose escalation can be continued. If symptoms during an up-dosing day require administration of more than 2 doses of an antihistamine or of an antihistamine in combination with other medications (except epinephrine), there should be a dose reduction of 1 or 2 dose levels, with the next dose given in the CRC. If epinephrine is administered, then a different course of action is to be taken.

- Epinephrine – General

Any reaction to IP (in clinic or at home) that requires 3 or more doses of epinephrine will halt all further dosing of IP for the individual. The subject will be asked to return to the CRC 14 to 16 days following the last dose of IP to undergo an Early Discontinuation Visit ([Section 6.4](#)).

- Epinephrine – Clinic

If administration of epinephrine is required during, or after, a dose-escalation in the clinic, or for anaphylaxis, no further dosing of IP is to occur at that visit. The next

dose of IP is to be reduced by 1 or 2 dose levels per investigator discretion based on the type and severity of allergy symptoms ([Section 6.7.5, Figure 3](#)), and administered in the CRC. After continuing the reduced dose for a duration of time recommended by the investigator, dose re-escalation at 1 dose level may be attempted in the CRC.

If epinephrine is administered for severe allergy symptoms, discussion with the medical monitor is strongly recommended.

If administration of epinephrine is required a third consecutive time, no further dosing should be attempted. Dosing in these subjects will be discontinued. They will be asked to return to the CRC 14 to 16 days following their last dose of IP to undergo an Early Discontinuation Visit ([Section 6.4](#)).

- **Epinephrine – Home**

Administration of epinephrine outside of the clinic should be followed immediately by the subject being taken to the nearest ER. The subject should return to clinic for a reduced dose (dose reduced by 1 or 2 dose levels per investigator discretion), administered under medical supervision prior to resuming any dosing at home. After continuing the reduced dose for a duration of time recommended by the investigator, dose re-escalation at 1 dose level may be attempted in the CRC.

If epinephrine is administered for severe allergy symptoms, discussion with the medical monitor is strongly recommended.

[figure not shown]

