Based on experience from Phase 2 studies, most acute allergic responses to dosing that are characterized by mild symptoms would be anticipated to meet the above criteria. If, however, an allergic response to dosing is characterized by mild symptoms that do not meet all of the above criteria (eg, has mild symptoms occurring in 2 or more organ systems, requires treatment with 2 doses of antihistamine or 1 dose epinephrine, shows progression in severity or distribution over time, is protracted in duration, or includes objective wheezing), then even though the allergic symptoms may be mild, the dose should be assessed as not tolerated. If a dose elicits mild symptoms that do not fit all of the above criteria and the dose is assessed to

be tolerated, then a brief explanation as to why the dose was considered tolerated must be recorded in the CRF.

Moderate symptoms: In general, if a dose elicits moderate symptoms, the dose will be assessed as not tolerated. However, there may be rare occasions when a dose eliciting moderate symptoms could be assessed as tolerated. This would only be the case for a transient, self-limited (requiring no intervention and resolving completely) symptom occurring in a single organ system. In addition, the symptom would be typically subjective only. Any dose associated with moderate symptoms and assessed as tolerated must be accompanied by a brief explanation in the CRF as to why the dose was considered tolerated.

Severe symptoms: In nearly all cases, if a dose elicits severe symptoms, the dose will be assessed as not tolerated. Whenever a dose elicits an allergic response characterized by 1 or more severe symptoms, the crucial decision, after adequate treatment for the allergic reaction has been administered, will be to determine whether the subject should continue in the study, dosing at a reduced dose level, or be discontinued early from the study.

The determination of tolerability will decide the course of action to be taken in response to dose-related reactions ([Section 6.7.3](#)).

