6.7.5 Treatment for Reactions During the Up-dosing Period: Dose Adjustment

If a dose or dose level is assessed as *not tolerated*, the action taken will depend on the type and severity of the dose-related reaction and the investigator's clinical judgment. The following possible actions are at the investigator's disposal and are considered in greater detail in subsequent sections ([Section 6.7.5.1](#), [Section 6.7.5.2](#), and [Section 6.7.5.3](#)):

- Dosing the subject under medical supervision in the CRC – this is encouraged whenever there is question as to the tolerability of a dose level. It may be performed at the current dose level or at a reduced dose level if there is already a high index of suspicion that the current dose level has not been tolerated.
- Holding dose level at current level for an additional 1 to 2 weeks before attempting dose escalation – this may be done at the discretion of the investigator if there is concern that the current dose level has not been sufficiently well tolerated to attempt up-doing to the next dose level.

[figure not shown]
- Reducing dose by 1 or 2 dose levels and maintaining the reduced dose level for at least 1 to 2 weeks before attempting dose re-escalation – Generally, this should be the action taken when a dose that has been observed in the CRC is assessed as not tolerated, if a dose elicits moderately severe symptoms, or if the investigator is convinced of the intolerance of the current dose level. In short, it should be considered the default action whenever a dose or dose level is assessed as *not tolerated*.
- Reducing dose level for less than the usual 2-week period – this may be instituted as treatment for an intercurrent AE, to aid the investigator in determining if a dose level is or is not tolerated, or if a pattern of decreased IP tolerability during menses is discerned. The level of the reduction in dose, ranging from a 1-step reduction to a 50% reduction will be at the investigator's discretion, based on clinical judgment. The manner in which dose escalation may resume will depend on the level and the duration of the dose reduction.

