- **Mild symptoms assessed as not tolerated:** If other *mild symptoms* occur with the first dose at a new dose level and the dose is *assessed as not tolerated*, the action taken should be to have the subject return to the CRC the next day for dosing at the last tolerated dose (ie, a 1-step dose reduction) under medical supervision (if the subject is unable to return to the CRC on the day specified, the investigator may initiate an approximate 1 dose-level reduction at home, with the subject coming to the CRC at the earliest date possible). If the reduced dose is *assessed as tolerated*, the subject is to continue on that daily home dose for at least 1 to 2 weeks. ([Section 6.7.5.2](#) for actions to be taken in the event that symptoms develop during home-dosing.) If the reduced dose is again *assessed as not tolerated*, the subject is to return to the CRC the next day for supervised dosing at a 1- or 2-step reduction in dose (per investigator judgment, based on severity of reaction). If this further reduced dose is *assessed as tolerated*, the subject will continue at that dose level for daily home-dosing over the ensuing 2 weeks. If, however, the reduced dose is *assessed as not tolerated*, the subject is to be considered an escalation failure non-responder.
- **Moderate symptoms:** If *moderate symptoms* occur with the first dose at a new dose level, except for rare instances, the dose will be *assessed as not tolerated*. The action taken should be to have the subject return to the CRC the next day for dosing at the last tolerated dose under medical supervision. If this reduced dose elicits no allergic symptoms (ie, is well tolerated), the subject will continue on that daily home dose

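### The antihistamine-only rule in 6.7.6 lets escalation continue after a moderate reaction that 6.7.2 and 6.7.5.1 treat as not tolerated

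*Protocol*

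**What the plan says.** Section 6.7.6 deals first with treatment and then with what follows it. On treatment, Table 5 and its text let the investigator give a moderate reaction either drug or both: "Generally, for moderate symptoms requiring treatment, the subjects should receive antihistamines and/or epinephrine, as indicated". Table 6 is introduced as the procedures "that should be implemented after treatment of a reaction experienced during the Up-dosing Period". Its first row, for antihistamines only, reads "Continue dose escalation", and the explanatory bullet repeats it: "If a subject receives antihistamines only, the dose escalation can be continued". The bullet's limits are more than two antihistamine doses in an up-dosing day, or an antihistamine combined with another medication. Either leads to a reduction of one or two levels (epinephrine has its own rules). The table row omits even these limits.

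The tolerability sections say something else. Section 6.7.2 generally classes a dose that elicits moderate symptoms as not tolerated and describes a rare exception: "This would only be the case for a transient, self-limited (requiring no intervention and resolving completely) symptom occurring in a single organ system". It adds: "The determination of tolerability will decide the course of action to be taken in response to dose-related reactions". Section 6.7.5 says of a reduction by one or two levels that "it should be considered the default action whenever a dose or dose level is assessed as" not tolerated. Section 6.7.5.1 gives one instruction both for mild reactions assessed as not tolerated and for moderate reactions: "the action taken should be to have the subject return to the CRC the next day for dosing at the last tolerated dose", under supervision. For doses at home, 6.7.3.1 also treats moderate symptoms as showing that the dose level is not tolerated.

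**The concern.** Table 6 chooses the next dosing step from the drug given, while 6.7.2, 6.7.5 and 6.7.5.1 choose it from severity and tolerability. The two approaches give opposite answers for a moderate reaction treated with one or two antihistamine doses and nothing else, and the protocol expressly allows that treatment.

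The cross-references make this more than an untidy summary. Sections 6.7.5.1 and 6.7.5.2 both send the reader to 6.7.6 for dose adjustment after antihistamines. A site that follows the pointer reaches the text without the condition.

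What is at stake is the safety of children aged 4 to 17 who take allergen daily, mostly at home, and consistent dosing between sites. A site applying Table 6 literally would keep a child on a dose that 6.7.2 classes as not tolerated, and then escalate from it. Section 6.7.7 carries the same rules into Maintenance.

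**Working it through.** The plan has no figure of its own to reproduce here. The check traces the possible cases through both sets of rules and then sizes the difference in dose.

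**Step 1. Trace by severity and number of antihistamine doses (no other drug).**

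| Reaction | Sections 6.7.2, 6.7.5, 6.7.5.1 | Bullet in 6.7.6 | Agreement |
|---|---|---|---|
| Moderate, 1 or 2 doses | Not tolerated; next dose at the last tolerated level in the clinic | Escalation may continue | No |
| Moderate, 3 or more doses | Not tolerated; step down | Reduce 1 or 2 levels | Yes |
| Mild, 1 oral dose, other criteria met | May be assessed as tolerated | Escalation may continue | Yes |
| Mild, 2 doses | Given as an example of not tolerated; override possible with an explanation in the CRF | Escalation may continue | Not fully |

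The first line is the finding. The exception for moderate reactions in 6.7.2 requires that no intervention was needed, so a reaction that required an antihistamine cannot use it. The last line is softer: 6.7.2 judges a single reaction and allows a documented override, while 6.7.6 counts antihistamine doses over an up-dosing day.

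**Step 2. Compare with neighbouring rules.** In Initial Escalation (6.7.4), continuing after one or two antihistamine doses is confined to mild symptoms. Stopping for a moderate reaction at any dose up to 3 mg depends on severity alone. Within Table 6, the rows for epinephrine given in the clinic or at home refer to 6.7.5 and Figure 3 and to the type and severity of symptoms. The antihistamine row has no such condition.

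**Step 3. Size of the dose difference.** The doses in Table 2 are 3, 6, 12, 20, 40, 80, 120, 160, 200, 240 and 300 mg. The ratio is the reacting dose divided by the dose one step below:

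6/3 = 2.00; 12/6 = 2.00; 20/12 = 1.67; 40/20 = 2.00; 80/40 = 2.00; 120/80 = 1.50; 160/120 = 1.33; 200/160 = 1.25; 240/200 = 1.20; 300/240 = 1.25.

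The range is 1.20 to 2.00. The dose is doubled at 4 of 10 steps (6, 12, 40 and 80 mg), and the ratio is at least 1.5 at 6 of 10. In Maintenance the comparison is 300 with 240 mg, or 1.25.

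**Step 4. How many children could meet the conflict.** Section 1.6 expects about 15% of subjects to have moderate symptoms at some point in dosing, and section 9.4 plans 120 subjects on AR101: 0.15 × 120 = 18. The protocol does not give the share treated with antihistamines alone, so it is assumed:

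- 25%: 0.25 × 18 = 4.5
- 50%: 0.50 × 18 = 9
- 75%: 0.75 × 18 = 13.5

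That is about 5 to 14 children at least once.

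**Step 5. Room in the schedule.** Up-dosing is nominally 20 weeks with a maximum of 40 (section 6.3.3), which leaves 40 − 20 = 20 spare weeks. One step down of about 2 weeks uses 2/20 = 10% of that.

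**The case against.** The strongest reply is that the protocol read as a whole already supplies the governing rule. Section 6.7.2 says tolerability decides the action. Section 6.3.3.1 ties dose adjustment to symptom severity through 6.7.5 and lets the investigator postpone an escalation. Section 6.7.5.2 sends home doses assessed as not tolerated to the 6.3.3 procedures, and 6.7.3.1 brings a child with moderate symptoms at home to the clinic the next day. The note under Table 5 points to 6.7.1 and 6.7.2. The bullet only permits continuation, so it could be read as saying that antihistamine use does not by itself bar escalation. Questions that the procedures leave open go to the medical monitor.

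This shows what was probably intended, and it lowers the chance that a site would go wrong. It does not remove the conflict. The note under Table 5 does not condition Table 6, whose row is an unqualified instruction. Permission to continue still contradicts the direction to step down.

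Three further points stand as limits on the finding. Figure 3, the up-dosing algorithm, is not visible in the text available and could not be checked. The dose ratios are the ordinary scheduled steps and do not measure harm. The count in Step 4 is of children exposed to conflicting wording; actual misdosing would also require the site to set aside 6.7.2, 6.7.5 and 6.7.5.1. The 15% comes from earlier oral immunotherapy studies and covers all dosing periods, including Initial Escalation, where there is no conflict, so for any assumed share the count is a rough upper figure.

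**Conclusion.** The concern holds. For a moderate reaction treated with one or two antihistamine doses, Table 6 and the bullet in 6.7.6 contradict 6.7.2, 6.7.5 and 6.7.5.1, and the version in 6.7.6 is the less safe one. The text is wrong as written; it is not a matter of detail left to another document.

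If 6.7.6 is followed, the child takes 1.2 to 2.0 times the dose that 6.7.5.1 points to. About 5 to 14 of 120 AR101 subjects might meet the situation, given the 15% rate in section 1.6 and the assumed 25% to 75% antihistamine-only share. Observed up-dosing and clinical judgment should keep actual misdosing below that. No statistical quantity changes, and any effect on the primary endpoint is likely to be small. The correction should be made because it protects children and makes dosing uniform across sites at very little cost.

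**What to change.** Limit the antihistamine-only row of Table 6 and the matching bullet to doses assessed as tolerated under 6.7.2. Send every antihistamine-only reaction assessed as not tolerated to 6.7.5.1, and state that this includes any moderate reaction that needed treatment. Leave the epinephrine rows and bullets unchanged.

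As a secondary edit, on which the main fix does not depend, set the antihistamine threshold for reduction in 6.7.6 at two or more doses to match 6.7.2. Keep the override with a CRF explanation, and carry the limit into the table row.

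The cost is new wording in one row and one bullet plus a clarification to sites. No extra subjects or procedures are needed. The downside is an occasional step down of about two weeks, which the up-dosing window can absorb.
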